11.1.2 Low Luminance Mobility Test (LLMT)

Low luminance mobility will be assessed by comparison of mean change in CIL scale scores from baseline. CIL scale scores will be summarized in Study Eye and Both Eyes at Baseline, Month 6 and Month 12. In addition, change from baseline will also be summarized using summary statistics for each post-baseline time point.

CIL scores will be converted to a scale score of -1 (cannot pass at the brightest light level) to 13 (does not slow even with room lights off). Conversion of CIL lux values to scale scores are included in the following table:

CIL (Lux)	Lights off	0.12	0.25	0.5	1.0	2.0	4.0	8.0	16	32	63	125	250	500	No Pass
Scale Score	13	12	11	10	9	8	7	6	5	4	3	2	1	0	-1

Subjects who cannot perform mobility testing at Baseline will be considered to have a scale score of -1 for CIL. The assignment of a -1 CIL scale score will be done during the programming of the analysis datasets.

11.1.3 Contrast Sensitivity Test (CST)

Contrast Sensitivity will be summarized for both Study Eye and Non-Study Eye at Baseline, Month 6 and Month 12 using descriptive statistics.

For any spatial frequency with more than one threshold value (or trial), the values will be averaged (mean), and a single mean value for that spatial frequency will be calculated. A single value trial at a spatial frequency indicates exploratory testing only and does not represent repeatable trials and will not be analyzed. Each of the mean threshold values is plotted per spatial frequency by the Beethoven instrument to create a curve. The highest mean threshold value for any of the spatial frequencies will be used to represent the nearest peak of the curve and will be called Peak Contrast Sensitivity and will be used for summary statistics. The spatial frequency at which the peak of the curve corresponds may vary from visit to visit or patient to patient. The threshold Peak Contrast Sensitivity value will be compared for the Safety population.

Change from baseline will also be summarized using summary statistics for each post-baseline time point.

Values for subjects who do not have a visit record at all post-baseline are considered to be close to missing at random (visit missed or assessment not attempted) and these missing values will not be imputed. Subjects with completely missing baseline values (e.g. no visit or assessment attempted) will be considered unevaluable for this analysis.

11.1.4 Kinetic Visual Fields (KVF)

Results from the KVF examination will be summarized for both Study Eye and Non-Study Eye at specified time points. The total VF area will be summarized at Baseline, Month 6 and Month 12. The mean change from baseline in the total VF area at Month 6 and Month 12 will also be summarized.

Total VF area is calculated by taking the sum of the adjusted calculated size for all individual field areas (i.e., islands) for a subject with the same visit, same eye, same date and same time. If a subject only has one stimulus size populated at a particular visit/date/time, that stimulus size

should be used to calculate the total VF area. If a subject has multiple stimulus sizes populated at a particular visit/date/time, then the size used at baseline should be used for comparison. If at baseline, a subject has a near normal visual field for the V4e target size (>10,000 deg²), then the next smaller size target should be used (e.g. III4e) to calculate the total VF area for that visit/date/time and that target sized used for all visit comparisons.

Subjects with completely missing baseline values (e.g. no visit or assessment attempted) or who are unable to perform the kinetic field testing at Baseline, will be considered not evaluable for this analysis.

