7.2.5 Visual Field Testing (performed at jCyte Low Vision Facility)

Subjects enrolled in the study may have a severely restricted visual field (e.g., 4 degrees in diameter) with or without eccentric islands in the mid to far-periphery in advanced RP, or they may have full visual fields but reduced photopic sensitivity in earlier stages of RP. The Octopus 900 will be used for kinetic visual field testing using a specified target of V4e for more severe subjects and a target of III4e and V4e for better seeing subjects. Target size will be selected based on baseline visit for each eye separately. Whatever target size(s) is/are selected, the same size will be used throughout the study on that particular eye.

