- Kinetic Visual Field Testing (performed at jCyte Central Testing Facility): The Octopus 900 will be used for KVF testing using a specified target of V4e for subjects with a more severely impaired visual field (<10,000deg²) and a target of III4e and I4e for better seeing subjects (>10,000deg²). Target size will be selected based on Baseline visit for each eye separately. Whatever target size(s) is/are selected, the same size will be used throughout the study on that particular eye.
- Contrast Sensitivity Test (performed at jCyte Central Testing Facility): A CST test measures the ability of a subject to distinguish between finer and finer increments of light versus dark (contrast). Contrast provides critical information about edges, borders, and variations in luminance. CST is correlated to performance on many real world tasks and tests that generate a curve or multiple sensitivity thresholds at varying grating sizes

(spatial frequency [SF]) provide an in-depth view of functional vision. Using the Beethoven System, multiple thresholds and varying spatial frequencies creating a curve will be measured monocularly and the peak of the curve will be compared over time. Each spatial frequency is tested up to seven times (thresholds) so the mean threshold at the peak CST for each eye will be compared over time.

For each eye, threshold CST values will be recorded for spatial frequencies from the following range: 0.25, 0.5, 1.0, 2.0, 4.0, 8.0 and 16.0 (not all frequencies will be tested for each eye for each subject). If a subject can test at more than one target size (or SF), then at least three SFs will be tested with multiple trials at each to determine the mean thresholds for each SF.

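### SAP 11.1.4 does not require a lone recorded visual field target to match the eye's baseline target, so an off-plan or partly recorded visit gives a cross-target change; the target lists also differ, undeclared

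*SAP*

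**What the plan says.** SAP 11.1.4 contains three rules for choosing the target on which total field area is calculated.

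- **Rule 1 (one size recorded).** "If a subject only has one stimulus size populated at a particular visit/date/time, that stimulus size" is the one used for the total area.
- **Rule 2 (several sizes recorded).** In that case "then the size used at baseline should be used for comparison".
- **Rule 3 (near-normal field).** This rule starts "If at baseline, a subject has a near normal visual field for the V4e target size (>10,000 deg²" and moves such an eye to the next smaller target, III4e being the example, with "that target sized used for all visit comparisons".

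The same section names the endpoint: "The mean change from baseline in the total VF area at Month 6 and Month 12 will also be summarized".

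On testing, Protocol 7.2.5 selects the target(s) for each eye at baseline and adds that "the same size will be used throughout the study on that particular eye". SAP 10.1.1 repeats this. Both assign V4e to more severely affected subjects. For the others, the protocol has "a target of III4e and V4e for better seeing subjects" and the SAP has "a target of III4e and I4e for better seeing subjects". The SAP draws the line at 10,000 deg²; the protocol gives no numeric cut-off.

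SAP Section 15, which lists changes from the protocol, mentions only the renamed mobility test and the dropped A-scan.

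**The concern.** Rules 2 and 3 tie the comparison to baseline, but Rule 1 does not. If an eye was analysed on III4e at baseline and only V4e was recorded at Month 6, Rule 1 supplies the V4e area and Rule 3 forbids it. No rule ranks one above the other, and none sets the visit aside. A programmer who follows Rule 1 subtracts a III4e area from a V4e area.

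The study has one arm, and Protocol 9.2 makes the injected eye's own baseline its control. If a larger target gives a larger measured field, a switch of target looks like a gain or loss of field with no change in the eye, and no comparator arm would reveal it.

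The disagreement over target lists is a second, separate problem. Rule 3 needs a baseline V4e area, yet SAP 10.1.1 does not list V4e for the better-seeing eyes to which the rule applies. The text therefore leaves unclear which target is the reference for those eyes.

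**Working it through.** The plan gives no figure to reproduce: 25 to 30 subjects is set by availability, and no SD or expected change is stated for field area. The check is to apply the rules literally and then size a mismatch under a stated assumption.

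**Step 1. Rules 1 and 2 applied to every recordable set.** The targets named across the two documents are V4e, III4e and I4e. Take the baseline analysis target as V4e or III4e and run through what might be recorded at follow-up.

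| Recorded at follow-up | Baseline target V4e | Baseline target III4e |
|---|---|---|
| V4e only | like-for-like | **V4e against III4e** |
| III4e only | **III4e against V4e** | like-for-like |
| I4e only | **I4e against V4e** | **I4e against III4e** |
| V4e and III4e | like-for-like | like-for-like |
| V4e and I4e | like-for-like | no rule answers |
| III4e and I4e | no rule answers | like-for-like |
| all three | like-for-like | like-for-like |

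Of 14 cases, 8 are like-for-like, 4 are cross-target and 2 have no answer. All four cross-target cases come from Rule 1. Whenever the baseline target is among those recorded, the result is sound. These are logical possibilities, not frequencies.

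**Step 2. When a cross-target case can arise.** Because testing is meant to keep each eye's target(s) fixed, it needs one of two things:
- the eye was tested with a target other than its selected one(s); or
- the eye has two targets, as both documents provide for better-seeing subjects, and only one was recorded at that visit.

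An eye tested with V4e alone at every visit is never affected.

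**Step 3. Conflict and gaps inside 11.1.4.**
- For an eye moved to III4e by Rule 3, a follow-up with only V4e or only I4e satisfies Rule 1 and breaks Rule 3.
- If a near-normal eye has only V4e at baseline, Rule 3 cannot be carried out, because there is no smaller-target area to use.
- If an eye has two targets at baseline and Rule 3 does not apply, the baseline size in Rule 2 is not unique.
- Areas are grouped by visit, eye, date and time. Two targets with different times in one visit each look like a single-size record, and nothing chooses between them.

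**Step 4. Target lists side by side.** For more severe subjects both documents have V4e. For better-seeing subjects the protocol has III4e and V4e, and the SAP has III4e and I4e. V4e is in the protocol only and I4e in the SAP only.

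**Step 5. Size of one mismatch.** The gap in area between V4e and III4e in the same eye is not in the documents. Assume III4e covers 50% to 90% of a V4e area of 10,000 deg², the SAP's own threshold. The gap is then 10,000 × (1 − 0.9) = 1,000 to 10,000 × (1 − 0.5) = 5,000 deg². With k mismatched eyes among n eyes contributing a change value, all in the same direction:

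shift in mean change = k × gap / n

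| k | n = 25 | n = 30 |
|---|---|---|
| 1 | 1,000/25 = 40 to 5,000/25 = 200 | 1,000/30 = 33 to 5,000/30 = 167 |
| 3 | 120 to 600 | 100 to 500 |

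All values are in deg². The shift is upward when follow-up used the larger target and downward when it used the smaller. It would be larger per eye if fewer than 25 eyes contributed.

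**The case against.** The strongest reply is that the plan already intends like-for-like comparison. Both documents fix the target for each eye, and Rules 2 and 3 are anchored to baseline. On that view a mismatch is an edge case and the defect is one missing condition. This stands as a limit on exposure. It does not remove the defect: the fixed-target sentence governs how eyes are tested, whereas 11.1.4 governs what is computed when the record falls short. There it states a rule that returns a cross-target value.

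Three stronger readings are tempting, and the documents do not support them.

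- *That the SAP lets the target vary freely between visits.* The fixed-target requirement in both documents rules this out.
- *That the differing target lists themselves mix targets within an eye.* Under either list an eye should keep its own target(s). Nor do the lists show that V4e was never run in better-seeing eyes: V4e may have been used at baseline to classify them. SAP 10.1.1 does not say, and detailed procedures are left to a manual that is not part of these documents.
- *That a near-normal eye with only V4e at baseline gives a biased change.* If V4e is recorded again, alone or with III4e, the result is V4e against V4e. The fault there is a rule that cannot be carried out.

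It is also fair to say that SAP Section 11 plans no formal efficacy evaluation, and that field listings by eye are planned. The listing layouts are not visible, so whether they would show the target is unknown.

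**Conclusion.** The point holds in a limited form. SAP 11.1.4 accepts a lone recorded target without checking it against the eye's baseline analysis target, and no rule excludes a non-matching visit from the change summary. Where testing departs from the fixed-target requirement, or only part of an eye's target set is recorded, the computed change is wrong, and for eyes under the near-normal rule it contradicts the same paragraph. The disagreement between Protocol 7.2.5 and SAP 10.1.1 is real and undeclared, but it is a separate inconsistency.

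The 33 to 200 deg² shift from one mismatched eye rests on the assumed gap and on 25 to 30 eyes contributing. With no SD given, it cannot be set against the expected spread. The number of affected eyes is unknown and could be zero. The effect is confined to a descriptive secondary endpoint; the primary safety objective is untouched. The change is worth making because it is cheap and the rule as written can return a wrong value.

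**What to change.** 1. Keep the single-size rule for the by-visit summaries of total area. Replacing it outright would leave single-target visits, including baseline, without a definition.
2. Define one analysis target per eye at baseline. State what applies when two targets were recorded and the near-normal rule does not apply, when a near-normal eye has only V4e, and when targets in one visit carry different times.
3. Compute change from baseline only on that target. Treat a visit without it as missing for change and list it with the target recorded. This agrees with SAP 10.3, which does not impute assessments that were not obtained.
4. Reconcile Protocol 7.2.5, SAP 10.1.1 and SAP 11.1.4 on the targets for better-seeing eyes and on where the baseline V4e area comes from. Record the difference in SAP Section 15.

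The cost is a few sentences of SAP text and one programming condition, best settled before database lock. A tabulation of recorded target by eye and visit would show whether any eye is affected. The downside is that a few change values may become missing.

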11.2 Exploratory Analyses

Exploratory endpoints include UBM, B-Scan, Slit lamp biomicroscopy and photography, SD-OCT of jCell, and FST.

Exploratory testing may occur at Baseline, Day 7, Day 28, Month 3, Month 6, Month 9 and Month 12 or Early Termination depending on what equipment is available.

Data on exploratory assessments will be provided in data listings only.

12. PHARMACOKINETIC ANALYSES

No pharmacokinetic analyses are planned for this study.

13. SAFETY ANALYSES

The primary endpoint of this study is to obtain safety profiles for reinjection of jCell. The safety analyses of AEs and laboratory parameters will include descriptive statistics. Summaries of AEs will be generated by type (AE or SAE), body system and PT, severity, and relationship to study product.

All safety analyses will be based on the safety population.

13.1 Study Drug Administration

Treatment compliance will be assessed via direct observation by the study investigator who is responsible for study drug administration. The exact time of injection will be recorded on the eCRF.

Study drug administration responses will be tabulated according to questions asked in the eCRF, including whether the total dose was administered, whether there were any dose interruptions, whether there were any AEs observed, whether the subject's vital signs are comparable to pre-treatment of study drug injection, the subject's IOP measurement post-treatment of study drug injection and whether the subject was prescribed topical treatment after treatment of study drug injection.

13.2 Adverse Events

All AE summaries will be restricted to treatment-emergent AEs (TEAEs), which are defined as those AEs that occurred after dosing and those existing AEs that worsened during the study. In the case of worsening in severity, a new entry is created in the database with start date equal to start of worsening. If it cannot be determined whether the AE is treatment-emergent due to a partial onset date, then it will be counted as such. Verbatim terms in the eCRFs will be mapped to SOCs and PTs using MedDRA, version 23.1.

AE summaries that are displayed by SOC and PTs will be ordered by descending subject count by SOC and PT within SOC. Summaries of the following types will be presented:

- Overall summary of TEAEs that contains a summary of the following:
 - Subject and event count of any TEAE
 - Subject and event count of TEAEs related to study drug
 - Subject and event count of serious TEAEs
 - Subject and event count of any serious TEAE related to study drug
 - Subject and event count of severe TEAEs related to study drug

Separate TEAE summary tables will be provided as follows:

- Subject incidence and event count of TEAEs by MedDRA SOC and PT.
- Subject incidence and event count of TEAEs by MedDRA SOC, PT, and highest severity. At each level of subject summarization, a subject is classified according to the highest severity if the subject reported more than one of the same event. Categories of severity will be "Mild", "Moderate", "Severe" and "Life threatening". Adverse events with missing severity will be assigned to "Severe" for this summary.
- Subject incidence and event count of TEAEs related to study drug by MedDRA SOC and PT. Related AEs are those reported as "Related" and "Possibly Related". At each level of subject summarization, a subject is classified according to the closest relationship if the subject reported more than one of the same event. Adverse events with a missing relationship will be considered related for this summary.
- Subject incidence and event count of serious TEAEs by MedDRA SOC and PT.

Separate listings of related TEAEs and SAEs will be provided.

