5.0 TREATMENT PLAN

5.1 Dose and Schedule

At the time informed consent is obtained, qualified subjects will be assigned a study number. All subjects will receive a single intravitreal injection of 6.0×10^6 hRPC into one previously treated eye. After topical anesthesia, a single 65 microliter suspension of cells will be delivered into the vitreous cavity using a 30 g needle. This treatment does not require surgical detachment or manipulation of the retina. The injection procedure itself takes approximately 2 minutes. Following 60 minutes of observation with no serious clinical symptoms or manifestations (IOP < 30 mm Hg and vital signs comparable to pre-treatment), subjects will be released to home on the day of injection. Please refer to the study procedure manual for details of patient preparation and monitoring.

The schedule of observations and assessments during the study is summarized in Table 2.

Table 2 Schedule of Assessme

Timepoint	Scr	BL*	Day 0	Day 1	Day 7 ³	Day 28 ³	M3 ⁴	M6 ⁴	M9 ⁴	M12 or Early Term ⁵
Written informed consent	Х									
Medical history (MH)	Х	x*								Х
Physical examination (PE)	Х	x*								Х
Brief MH and PE				Х	X	Х	Х	х	Х	
Vital signs	Х	Х	Х	Х	X	Х	Х	х	Х	Х
Pregnancy test	Х	x*								Х
Safety laboratory tests ¹	Х	x*				Х	Х	х		Х
Urinalysis	Х	x*					Х	х		Х
Slit lamp and fundus exam	Х	Х		Х		Х	Х	х	Х	Х
Optos photography		Х		х		х	Х	х	Х	Х
BCVA (E-ETDRS)	х	Х	Х	х	х	х	Х	х	Х	Х
IOP		Х	Х	х	х	х	Х	х	Х	Х
OCT		Х								Х
VF		Х						х		Х
Exploratory Testing (optional) ⁶		Х			Х	Х	Х	Х	Х	Х
Contrast sensitivity		Х						Х		Х
Mobility test		Х						х		Х
Study Drug Injection			Х							
Con Meds			Х	Х	Х	Х	Х	Х	Х	Х
Adverse events			Х	Х	Х	х	Х	Х	Х	Х
Blood sample for Ab testing ²		Х				х		Х		

¹Hematology (minimally Hct, Hgb, CBC with diff, plt), coagulation panel (screening only) and blood chemistries (minimally AP, ALT, AST, BUN, Cr, total bilirubin, serum electrolytes, glucose, calcium, phosphate, albumin, total protein and HbA1c) ² Testing for Panel Reactive Antibodies (PRA) and Donor Reactive Antibodies (DRA)

³ visit window +/- 1 day ⁴ visit window +/- 4 days ⁵ visit window +/- 10 days

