7.0 ASSESSMENTS

7.1 Safety Assessments

7.1.1 Adverse Events

Subjects will be monitored for AEs from the time the subject receives a subject number until the study end or early termination. Adverse events that occur between clinic visits will be elicited by direct, non-leading questioning or will be recorded if offered voluntarily by the subject. Further details for AE reporting can be found in Section 9.

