8.0 SAFETY CONSIDERATIONS

8.1 Adverse Events

An AE is defined for this study as any untoward medical occurrence in a subject who is administered clinical study material. The occurrence of this event does not necessarily have a causal relationship with study product. An AE can therefore be any unfavorable and unintended sign (including an abnormal laboratory finding), symptom, or disease temporally associated with the use of a study (investigational) product or treatment (e.g. mock injection), whether or not related to the study product or treatment. CONFIDENTIAL 30 of 37 Examples of an AE include:

- Exacerbation of a chronic or intermittent pre-existing condition, including either an increase in frequency or intensity of the condition
- Significant or unexpected worsening or exacerbation of the condition/indication under study (RP)
- A new condition detected or diagnosed after study product administration even though it may have been present prior to the start of the study
- Signs, symptoms, or clinical sequelae of a suspected overdose of either study product or a concurrent medication
- Pre- or post-treatment events that occur as a result of protocol-mandated procedures
- Antibody development

An AE does **not** include:

- Medical or surgical procedures (e.g., colonoscopy or biopsy); the medical condition that leads to the procedure is an AE
- Social or convenience hospital admissions where an untoward medical occurrence did not occur
- Day-to-day fluctuations of a pre-existing disease or conditions present or detected at the start of the study that do not worsen
- The disease/disorder being studied (RP), or expected progression, signs, or symptoms of the disease/disorder being studied unless more severe than expected for the subject's condition

All AEs that occur after informed consent is signed will be recorded in the source documents and on the appropriate CRF page. The information to be collected includes the nature, date and time of onset, intensity (mild, moderate, severe, life-threatening, death), duration, causality (relationship to investigational product), and outcome of the event. Even if the AE/SAE is assessed by the Investigator as not reasonably attributable to study product, its occurrence must be recorded in the source documents and on the appropriate page of the CRF.

Treatment-emergent AEs will be defined as AEs that occur after the study treatment (injection or mock injection).

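### SAP 13.2 ties its worsening limb to the study rather than the injection, so, programmed literally, an AE that starts and worsens between consent and Day 0 would enter the TEAE tables

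*SAP*

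**What the plan says.** SAP 13.2 limits all AE summaries to TEAEs and defines them as "those AEs that occurred after dosing and those existing AEs that worsened during the study". For a worsening in severity, it adds that "a new entry is created in the database with start date equal to start of worsening".

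Protocol 8.1 has a single limb: "Treatment-emergent AEs will be defined as AEs that occur after the study treatment".

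The protocol opens AE collection before the injection. Section 8.1 states: "All AEs that occur after informed consent is signed will be recorded". Section 7.1.1 states: "Subjects will be monitored for AEs from the time the subject receives a subject number until the study end or early termination". Section 5.1 places that number at consent: "At the time informed consent is obtained, qualified subjects will be assigned a study number".

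SAP 15 declares two changes from the protocol, the renamed mobility test and the dropped A-scan. The TEAE definition is not among them.

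**The concern.** The two documents define the central safety term differently. The SAP version, taken at its word, admits events that began before the second injection.

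The term matters here. SAP 13 makes the safety profile of reinjection the primary endpoint, and Protocol 3.2.2 lists TEAE incidence and severity first among the safety criteria. The study has one arm, so no control group carries the same pre-dose events. SAP 5 justifies the sample size by the ability to judge consistency with earlier first-eye and fellow-eye treatments. An inflated numerator would be carried into that judgement.

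**Working it through.** The plan states no figure that depends on this definition, and the 25 to 30 subjects rest on availability, so there is no planned number to reproduce. The check is of date logic, followed by simple sizing.

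**Inputs**
- TEAE definitions: SAP 13.2 and Protocol 8.1.
- Start of AE recording: consent (Protocol 8.1), or subject number (7.1.1), which is assigned at consent (5.1).
- Record for a worsening in severity: a new entry with its own start date (SAP 13.2).
- Time from screening to injection: some tests need no repeat if Day 0 falls within 30 days of screening (notes to Table 2, Protocol 6.2). No maximum interval is stated.
- Denominator: 25 to 30 subjects (SAP 5).

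**Step 1: classify four example records.** Days are relative to the injection. The protocol counts a record if its start is after the injection. The SAP as written counts it if its start is after the injection, or if it is the worsening of an existing AE.

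| Record | Protocol 8.1 | SAP 13.2 as written | SAP with worsening tied to dosing |
|---|---|---|---|
| New AE, day -10 | no | no | no |
| AE from day -20, worsening entry day -5 | no | **yes** | no |
| AE from day -20, worsening entry day +5 | yes | yes | yes |
| New AE, day +3 | yes | yes | yes |

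The documents disagree on one record, the pre-injection worsening. The third row shows why: a worsening after the injection has a post-injection start date and already meets the first limb. For fully dated worsening in severity, the second limb therefore adds only entries from before the injection. With the limb tied to dosing, the two documents agree on all four.

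**Step 2: size per subject.** The contribution of k subjects counted only for this reason is k/N.
- N = 25: 1/25 = 4.0, 2/25 = 8.0, 3/25 = 12.0 percentage points.
- N = 30: 1/30 = 3.3, 2/30 = 6.7, 3/30 = 10.0 percentage points.

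Subjects are counted once per level. The increment therefore arises only if the subject has no qualifying post-dose event at that system organ class or preferred term level.

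**Step 3: chance that it happens at all.** The documents give no frequency. If a proportion p of subjects has such a worsening (an assumption), the chance of at least one is 1 - (1 - p)^N.

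| Assumed p | N = 25 | N = 30 |
|---|---|---|
| 1% | 22% | 26% |
| 3% | 53% | 60% |
| 5% | 72% | 79% |

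These rates only illustrate the range; nothing in the documents supports one over another.

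**The case against.** **Intent.** The strongest reply is that the surrounding text classifies by onset date. SAP 13.2 counts an event as treatment-emergent when a partial onset date leaves its status undetermined. Appendix A places missing or incomplete onsets in the treatment phase unless other data show otherwise. A separate start date for each worsening also makes most sense if records are compared with the injection date. This stands as evidence that post-dose worsening was meant. It does not repair the text, because those rules govern incomplete dates, and a fully dated worsening on day -5 falls under the definition alone.

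**Pre-existing conditions.** A reader might infer that any condition present at consent that worsens before Day 0 is caught. The documents do not support that. Such conditions are collected as medical or ocular history, and a first worsening before the injection would be a first AE record, which is not clearly an existing AE that worsened. The limb clearly applies only when an AE both starts and worsens between consent and injection.

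**Attribution.** A reader might also infer that the rule attributes pre-dose events to the injection. It does not: treatment-emergent status is about timing. The related-event table takes events that the investigator reports as related or possibly related, plus those with the relationship missing. A pre-injection worsening reaches it only by one of those routes.

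**Collection.** The AE row of Table 2 starts at Day 0, and Protocol 6.3 lists AEs on that day only after administration. Sites that worked from these would hold few pre-dose records. This stands and lowers the likely impact. It is a separate under-collection question and does not add to the over-count.

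**Consequence.** The analyses are descriptive, no numerical threshold depends on them, and the index includes a general AE listing (16.2.6.1) in which pre-dose records of treated subjects should be visible. The error over-counts and does not hide harm. These points limit the consequence but leave the conflict in the primary safety tables.

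**Conclusion.** The concern holds as a conflict of definition. SAP 13.2 is wider than Protocol 8.1, the difference is undeclared, and for fully dated worsening in severity the extra limb adds only pre-injection entries. They would enter the TEAE tables if the sentence were programmed literally; the documents do not show that it will be.

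Each subject counted only for this reason adds 3.3 to 4.0 percentage points at a given level, upwards. This assumes 25 to 30 treated subjects and no qualifying post-dose event at the same level. The frequency is unknown and probably low. The conclusion covers worsening in severity, the only kind for which the SAP creates a new entry. A correction is worthwhile because the tables concerned are the primary output and the change is small.

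**What to change.** - In SAP 13.2, change the second limb to *existing AEs that worsened in severity after study drug administration*.
- Classify every AE record, including each worsening entry, by its own start date and time against the recorded injection time. This settles events on Day 0 itself.
- Flag pre-injection AEs and worsenings in the AE listing (16.2.6.1).
- If the wider definition is intended, declare and justify it in SAP 15.
- Separately, reconcile the AE row of protocol Table 2 with Protocol 7.1.1 and 8.1 on when AE collection starts. The SAP is dated 9 November 2022 and the planned study period ended in Q3 2022, so this may come too late to change collection. In that case the study report should state from when AEs were in fact recorded.

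The SAP change costs one phrase, a classification rule and a listing flag. It needs no new data: Protocol 8.1 already collects the date and time of onset, and Protocol 5.2 and SAP 13.1 require the exact time of injection.
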